11.4.3 Vital Signs

Body temperature, systolic blood pressure, diastolic blood pressure, heart rate and weight are collected at all visits. Height is collected at Screening.

The absolute values of the vital signs and weight will be summarised at each visit (*Table 14.3.3*). Height will be summarised within the demography data.

11.4.4 Physical Examination

A physical examination will be conducted at all visits.

Physical examination data will be listed only.

11.4.5 12-Lead ECG

A 12-lead ECG will be completed at baseline, Day 28, Day 56 and EOS.

The number and percentage of the patients with Normal / Abnormal NCS / Abnormal CS ECG results will be summarised at each visit (*Table 14.3.4.1*). A shift table will be presented, for patients with at least one Abnormal CS value, showing changes from baseline to each visit (*Tables 14.3.4.2*).

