1.2.5. Preclinical data of ABX464

1.2.5.1. Non-clinical background information

1.2.6. Previous clinical experience with ABX464

2. STUDY OBJECTIVES AND ENDPOINTS

2.1. Primary Objective

The primary objective of the study is to evaluate the safety of ABX464 given at 50 mg once daily versus Placebo in subjects with Moderate to Severe Active Ulcerative Colitis who have failed or are intolerant to immunomodulators, Anti-TNFα, vedolizumab and/or corticosteroids.

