9.3. Safety Analyses

Adverse events will be coded using the standard dictionary (MedDRA) down to the lower level term (LLT).

An overall summary table will be presented (Any adverse event, any treatment emergent adverse event (TEAE), any serious adverse event (SAE), death, any grade 3 or higher adverse events from baseline to the end of Study. This analysis will be conducted on SAF population.

Two periods will be defined for TEAE:

- Any adverse event which occurs or worsens from first dosing to Day 56;
- Any adverse event which occurs after Day 56.

Adverse events will be described by primary system organ class and preferred term. Numbers and percentage of subjects, and number of occurrence of adverse event will be presented for:

- TEAE:
- Serious TEAE;
- TEAE leading to drug discontinuation;
- TEAE of grade 3 or 4;
- TEAE for which relationship with the study drug is recorded as possible or probable.

Analysis of safety will be performed on the safety data set consisting all subjects who received at least one dose of ABX464 in the study.

Primary safety endpoint, the rate of all treatment emergent adverse experiences will be compared between the study groups by stratified likelihood ratio chi-square test on a 10% one-sided significance level.

Further assessment of safety will be based on the frequency of adverse events (with and without regard to causality) graded according to the CTC-AE Classification and also, the review of individual values for clinical laboratory data, vital signs and ECG focusing on the detection of abnormal values and PCSAs [potentially clinically significant abnormalities (PCSAs) determined upon investigator considerations].

Adverse events will be tabulated (counts and percents) by group. All adverse events will be listed and the data will be tabulated by body system/organ class. Adverse event tabulations will include all treatment emergent adverse events, which will be further classified by severity, and relationship to treatment and dose level.

Clinical laboratory parameters, vital signs, ECG will be summarized by using descriptive statistics (n, mean, SD, SEM, median, minimum and maximum). Number of subjects with at least one abnormal values will be tabulated (counts and percents) for each parameter in summary shift tables, by group and dose.

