11.4.2 Laboratory Data

The following routine clinical laboratory tests will be carried out throughout the study.

- Haematology: haemoglobin, haematocrit, white blood cells (WBC), neutrophils, lymphocytes, monocytes, eosinophils, basophils, platelet count, ESR
- Biochemistry: sodium, potassium, calcium, phosphate, glucose, blood urea nitrogen (BUN)
 /urea, creatinine, aspartate transaminase (AST), alanine transaminase (ALT), GLDH, lipase,
 alkaline phosphatase, gamma-glutamyl-transferase (GGT), total bilirubin, total protein, albumin,
 lactate dehydrogenase (LDH), CRP, T3, T4, TSH
- Stools: faecal calprotectin

The absolute values of each parameter and changes from baseline will be summarised at each visit (*Tables 14.3.2.1.1 to 14.3.2.1.3*). Laboratory parameters classified as normal/ abnormal non clinically significant (NCS)/ abnormal clinically significant (CS) will be presented in a shift table showing changes from baseline to each visit for patients with at least one abnormal CS value (*Tables 14.3.2.2.1 to 14.3.2.2.3*).

If laboratory results are repeated at the same visit, the repeated result will be used in summaries (instead of the original one) provided the sample was taken within the visit window, otherwise the original result will be used. All results will be listed.

Laboratory results at unscheduled visits will be included in the listings but will not be summarised.

Pregnancy data will be listed only.

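### The protocol promises numeric ECG summaries and abnormal-value counts for vital signs and ECG; the SAP omits the ECG numbers and the vital-sign counts without explanation, so a group-level shift in ECG intervals could not be seen

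*SAP*

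**What the plan says.** Safety is the trial's main purpose (Protocol 2.1): "The primary objective of the study is to evaluate the safety of ABX464 given at 50 mg once daily versus Placebo".

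Protocol 9.3 makes three commitments that cover ECG and vital signs:

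- Numeric summaries: "Clinical laboratory parameters, vital signs, ECG will be summarized by using descriptive statistics (n, mean, SD, SEM, median, minimum and maximum".
- Counts, in the next sentence: "Number of subjects with at least one abnormal values will be tabulated (counts and percents) for each parameter in summary shift tables".
- Individual review: "review of individual values for clinical laboratory data, vital signs and ECG focusing on the detection of abnormal values and PCSAs".

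The SAP plans the following:

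- ECG (11.4.5): "The number and percentage of the patients with Normal / Abnormal NCS / Abnormal CS ECG results will be summarised at each visit". It adds: "A shift table will be presented, for patients with at least one Abnormal CS value, showing changes from baseline to each visit".
- Vital signs (11.4.3): "The absolute values of the vital signs and weight will be summarised at each visit".
- Laboratory data (11.4.2), for contrast: "The absolute values of each parameter and changes from baseline will be summarised at each visit", plus shift tables.

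**The concern.** A mean and SD cannot be computed from a three-level investigator judgement. The protocol's ECG commitment therefore only makes sense if numeric ECG parameters are analysed, and the SAP analyses none. Each ECG is reduced to normal, abnormal not clinically significant, or abnormal clinically significant. An interval that lengthens in many treated subjects while each tracing keeps its category leaves that table unchanged.

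For vital signs the numbers are summarised, but the promised count of subjects with at least one abnormal value per parameter is missing.

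The stake is what the report can claim. In a trial whose primary objective is safety, a quiet category table could be read as showing no ECG effect when intervals were never examined in the way the protocol set out.

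**Working it through.** The plan states no figure on this point, so the check compares the protocol's commitments with the SAP text, table list and shells.

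**1. Numeric ECG summary.** Promised in Protocol 9.3. SAP 11.4.5 and the shell for Table 14.3.4.1 hold only counts and percentages in the three categories. Listing 16.4.9 has treatment, patient, visit, date, time, investigator's interpretation and abnormality, with no interval column. Result: absent from every planned ECG output.

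**2. ECG abnormal-value counts.** Promised for each parameter, for any abnormal value. The SAP has per-visit category counts for the ECG as a whole, and a shift table restricted to patients with at least one clinically significant abnormality. A patient who moves from normal to abnormal not clinically significant, and never has a clinically significant value, is counted at that visit in Table 14.3.4.1 but is left out of shift Table 14.3.4.2. Result: partly met. (SAP 11.4.2 puts the same restriction on the laboratory shift tables.)

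**3. Numeric vital-sign summary.** Promised. Table 14.3.3 gives N, mean, SD, median, minimum and maximum by arm, at baseline and each visit, for systolic and diastolic pressure, heart rate, temperature and weight. Result: met, apart from SEM.

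**4. Vital-sign abnormal-value counts.** Promised for each parameter in shift tables. SAP 11.4.3 has none, the table list in 14.1 has none, and the shift-table shell covers haematology, biochemistry, stool results and ECG only. Listing 16.4.7 gives individual values without a normal/abnormal column. Result: absent.

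**5. Explanation.** Protocol section 9 presents the SAP as a fuller working-out of the protocol's own features, with later SAP changes to be justified before final lock. The SAP gives no reason for items 1, 2 and 4, and its section 10.4 reports nothing to discuss.

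**6. Are the ECG numbers available?** Protocol 5.3.3 requires a 12-lead tracing at Day -14, Day 0, Day 28, Day 56 and EoS, kept at site as source data. It requires abnormal findings in the CRF and names no interval. QTc appears only in the abbreviation list, and the eCRF is not among the documents. Availability is therefore unknown.

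**7. Size of a transcription.** 30 subjects x 5 scheduled ECGs = 150. This is close to an upper limit, because Protocol 5.2.6 gives the EoS visit only to subjects who do not enter ABX464-102 (although 7.3 asks it of all). Replaced subjects could add a few.

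**The case against.** The best defence has four parts.

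- **Endpoint.** The primary endpoint is treatment-emergent adverse events, and ECG and vital signs are in neither document's endpoint list. Clinically relevant ECG changes from Day 0 and clinically significant vital-sign deviations must be recorded as adverse events (Protocol 5.3.1, 5.3.3), so they reach the TEAE tables. This stands, and it lowers the weight of the point. But SAP 4.4 names both as safety variables, and adverse-event reporting rests on judgement of one patient at a time; it does not replace a group summary.
- **Investigator judgement.** Protocol 9.3 leaves potentially clinically significant abnormalities to the investigator, and the SAP's categories fit that. This stands for the categories, not for the promised mean and SD.
- **Flexible outputs.** SAP 10.1 says eCRF data will be listed, and section 15 lets layouts change. If intervals are captured, they could be listed. A listing still gives no summary by arm.
- **Not promised.** Protocol 9.3 does not promise change from baseline for vital signs, nor any QTc limit. This stands: the first is offered below only as an extra, and no limit is proposed.

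A reader might also infer more than the documents support:

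- *That a blood-pressure shift would be hidden, or that heart rate is not reported.* Both are summarised numerically in Table 14.3.3 and listed in 16.4.7.
- *That the interval values are known to exist.* No section says they are measured, printed or entered.
- *That the trial could show or exclude a QTc shift of 10 to 15 ms.* The standard error of a between-arm difference is SD x sqrt(1/20 + 1/10) = 0.387 x SD, but the documents give no SD. If one assumes 12, 15 or 20 ms, the 90% half-widths with t(28) = 1.701 are 7.9, 9.9 and 13.2 ms. With no true shift, the upper limit falls below 10 ms only if the estimate is below about 0.1 ms at SD 15 (probability about 51%), or below -3.2 ms at SD 20 (about 34%). No such precision can be claimed.

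**Conclusion.** The point holds as an unexplained departure of the SAP from Protocol 9.3, in three places: no numeric ECG summary, an ECG shift table narrower than promised, and no abnormal-value counts or shift table for vital signs. The missing SEM is trivial.

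The consequence is specific to ECG intervals: a group-level shift could not be seen in any planned output. For vital signs the loss is smaller, since mean shifts remain visible and only the per-subject abnormal counts are lacking.

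The conclusion rests on the text and shells alone and needs no assumed variability. Whether the ECG gap can be closed depends on whether intervals are in the eCRF or readable from the printouts, which the documents do not settle. It should be resolved before database lock.

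**What to change.** **SAP 11.4.3 (vital signs).** Add, for each parameter, the number and percentage of subjects with at least one abnormal value, in a shift table by arm. State how abnormal is decided: Protocol 5.3.1 refers to a normal range but gives no limits, so the sponsor must name the range or use the investigator's classification if it is recorded. Add change from baseline to Table 14.3.3 as an extra, since the data are already collected, and SEM.

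**SAP 11.4.5 (ECG).** Remove the restriction of the shift table to patients with a clinically significant abnormality. If intervals are in the eCRF, or can be transcribed from the stored printouts, add numeric summaries of absolute value and change from Day 0 by arm and visit, and add the values to Listing 16.4.9.

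**If intervals cannot be captured.** Amend Protocol 9.3, or document and justify the departure in the SAP before database lock. Do not report the category table as evidence of no interval effect.

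**Cost.** The vital-sign part needs one new table, extra rows in another and SAP wording. The ECG part needs one new table, added listing columns and, if transcription is required, eCRF fields and site data entry for about 150 ECGs at most.

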11.5 STUDY DRUG EXPOSURE AND COMPLIANCE

Number of dose intakes and study drug exposure (days) will be summarised using descriptive statistics for the FAS (*Table 14.3.5*).

Treatment exposure is the number of days during the treatment period that the patient was exposed to the study treatment and is calculated as (date of last dose) - (date of first dose) + 1.

11.6 PRIOR AND CONCOMITANT MEDICATION

All medications taken by patients on entry to the study or during the study will be recorded in the eCRF. Medications will be classified using the version of the World Health Organisation Drug Dictionary (WHODD) coding dictionary defined in the DMP. The Anatomical Therapeutic Chemical (ATC) Classification and WHO-DRUG PT will be used to list and summarise the data.

Prior medications are defined as all medications that started and stopped before date of first dose. Only medications where the stop date is prior to date of first dose will be considered prior. If the stop date is unknown or incomplete and the medications cannot definitely be considered as stopped prior to date of first dose then the medications will be considered as concomitant medications.

Concomitant medications are defined as all medications that started on or after date of first dose.

The number (%) of patients reporting the use of any prior medications and the number (%) of patients taking each drug by ATC classification (1st, 2nd and 4th levels) and PT will be summarised using the FAS (Table 14.3.6.1).

This table will be repeated for concomitant medications (Table 14.3.6.2).

[figure not shown]

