3. INVESTIGATIONAL PLAN

3.1. Study design

3.1.1. Design and methodology

This Phase IIa study is an 8-week, double-blind, placebo-controlled, randomized study aimed at evaluating the safety and the efficacy of ABX464 given once a day (o.d) at 50 mg in subjects with moderate to severe Active Ulcerative Colitis who have failed or are intolerant to immunomodulators, Anti-TNF α , vedolizumab and/or corticosteroids followed by a one-month follow-up period.

Eligible subjects will be randomized according to a 2/1 ratio in two different groups of treatments according to the following study design.

Upon screening visit (D-14), eligible subjects will be checked for eligibility.

Subject eligibility will be confirmed by the medical staff based of the endoscopy central reading and on the laboratory results performed at screening visit. If eligibility is confirmed, then the subject will be randomized using the eCRF.

At Day 0, study drug (ABX464 or its matching placebo) will be added on top of this background therapy for the next 56 days. ABX464 or its matching placebo will be given once a day at 50 mg.

For subjects receiving oral corticosteroids during the study treatment period, tapering of steroids should start at week 4 at a rate of prednisone or prednisone equivalent 5 mg/week for 4 weeks to discontinuation. However, this study procedure is left to the Investigator's discretion.

The dose of 50 mg of the study drug has been selected based on the reassuring safety data accumulated on the 50 mg o.d. from previous studies and the high exposure in ABX464-NGluc (active metabolite) at this dose.

Eligible subjects will be randomized according to a 2/1 ratio in two different groups of treatments.

Randomization will be stratified according to the following factors: concomitant treatment with corticosteroids and previous TNF antagonist exposure.

Randomized subjects will be seen at the investigational site every week during the first month of treatment and then every two weeks during the second month. Flexible sigmoidoscopy with rectal and/or sigmoidal biopsies will be performed again at week 8.

The DSMB will meet after every 3 subjects are recruited in order to review on a regular basis the safety profile of this dose level and to recommend, if appropriate, the continuation of the study.

The sample size in this Proof of Concept study is 20 subjects receiving ABX464 and 10 subjects receiving Placebo (i.e. a total of 30 subjects).

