4.2. Eligibility Criteria

4.2.1. Inclusion Criteria

A subject will be eligible for inclusion in this study only if ALL of the following criteria apply:

- Men or women age 18 75 years;
- Diagnosis of moderate to severe active UC confirmed by endoscopy and histology at least 12 weeks prior
 to screening visit. Moderate to severe active UC defined by Mayo Clinic Score (MCS) of 6 to 12 inclusive (on
 a scale of 0-12). Moderate to severe active UC should be confirmed at screening visit with a centrally read
 MCS endoscopy score of at least 2 (on a scale of 0-3);
- Subjects receiving oral corticosteroids must have been on a stable dose of prednisone or prednisone equivalent ≤20 mg/day) or on beclomethasone diproprionate (≤5mg/day) or on budesonide MMX (≤9mg/day), for ≥2 weeks before the screening visit;
- Topical corticosteroids and topical 5-aminosalicylic acid preparations must have been withdrawn ≥2 weeks before the screening visit due to inefficacy or intolerance;
- Subjects who are on oral 5-aminosalicylic acid must have been on a stable dose ≥4 weeks before the screening visit;
- Subjects who are receiving immunosuppressants in the form of azathioprine, 6-mercaptopurine, or methotrexate needed to be on a stable dose for 4 weeks before the screening visit. Subjects taking methotrexate also are advised to take folic acid 1 mg/day (or equivalent) supplementation if there is no contraindication;
- Subjects on probiotics (e.g., Culturelle® [Lactobacillus GG, i-Health, Inc.], Saccharomyces boulardii) must be
 on stable doses for 2 weeks before the screening visit;
- Subjects on antidiarrheals (e.g., loperamide, diphenoxylate with atropine) must be on stable doses for 2 weeks before the screening visit;
- Subjects who have previously received anti-tumor necrosis factor (TNF) therapy or vedolizumab must have discontinued therapy ≥8 weeks before the screening visit due to inefficacy or intolerance;
- Subjects previously treated with cyclosporine or tacrolimus must have discontinued therapy ≥4 weeks before the screening visit due to inefficacy or intolerance;
- Subjects previously treated with tube feeding, defined formula diets, or parenteral alimentation/nutrition must have discontinued treatment 3 weeks before the screening visit;
- Subjects with hematological and biochemical laboratory parameters as follows and within 14 days of baseline:
 - Hemoglobin > 9.0 g dL-1;
 - Absolute neutrophil count ≥ 750 mm⁻³;
 - Platelets ≥ 100,000 mm⁻³;

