Diastolic BP (mmHg) Heart Rate (bpm)				
Body temperature (°C) Weight (kg)				
ource: Listing 16.x.x ath\Filename				Page x/y

Version date: 23 August 2018

Page 59 of 93

ABX464-101

Table 14.3.4.1 12-Lead Electrocardiogram (Safety Set)

ddMMMyyyy

		ABX-464	Placebo	Total
		(N=xx)	(N=xx)	(N=xx)
Baseline	N	xx	xx	xx
	Normal	xx (xx.x%)	xx (xx.x%)	xx (xx.x%)
	Abnormal NCS	xx (xx.x%)	xx (xx.x%)	xx (xx.x%)
	Abnormal CS	xx (xx.x%)	xx (xx.x%)	xx (xx.x%)

Etc

Source: Listing 16.x.x

Path\Filename

Page x/y

Version date: 23 August 2018

Page 60 of 93

GROUP

ABX464-101

Table 14.3.5 Study Drug Exposure (Full Analysis Set)

ddMMMyyyy

		ABX-464 (N=xx)	Placebo (N=xx)	Total (N=xx)
Number of dose intakes	N	xx	××	xx
	Mean	xx.xx	xx.xx	xx.xx
	SD	xx.xx	xx.xx	xx.xx
	Median	xx.xx	xx.xx	xx.xx
	Minimum	xx.x	xx.x	xx.x
	Maximum	xx.x	xx.x	xx.x
Study drug exposure (days)	N	xx	xx	xx
orday and exposure (days)	Mean Etc	xx.xx	xx.xx	xx.xx

Study drug exposure (days) is calculated as (date of last dose) - (date of first dose) + 1

Source: Listing 16.x.x

Path\Filename Page x/y

Version date: 23 August 2018

Page 61 of 93

Table 14.3.6.1 Prior Medications (Full Analysis Set)

ddMMMyyyy

	ABX - 464	Placebo	Total
www.	(N=xx)	(N=xx)	(N=xx)
Any prior medication	xx (xx.x%)	xx (xx.x%)	xx (xx.x%)
X, xxxxxxxxxxxx	xx (xx.x%)	xx (xx.x%)	xx (xx.x%)
XON, xxxxxxxxxxxx	xx (xx.x%)	xx (xx.x%)	xx (xx.x%)
XONXX, xxxxxxxxxxx	xx (xx.x%)	xx (xx.x%)	xx (xx.x%)
xxxxxxxxxxx	xx (xx.x%)	xx (xx.x%)	xx (xx.x%)
Etc	xx (xx.x%)	xx (xx.x%)	xx (xx.x%)
XONXX, xxxxxxxxxx	xx (xx.x%)	xx (xx.x%)	xx (xx.x%)
xxxxxxxxxxx	xx (xx.x%)	xx (xx.x%)	xx (xx.x%)
Etc	xx (xx.x%)	xx (xx.x%)	xx (xx.x%)
XON, xxxxxxxxxxxx	xx (xx.x%)	xx (xx.x%)	xx (xx.x%)
XONXX, xxxxxxxxxxx	xx (xx.x%)	xx (xx.x%)	xx (xx.x%)
xxxxxxxxxx	xx (xx.x%)	xx (xx.x%)	xx (xx.x%)
Etc	xx (xx.x%)	xx (xx.x%)	xx (xx.x%)

Etc

Version date: 23 August 2018

Page 62 of 93

¹ Medication that stopped prior to date of first dose

WHO-DDE version <XX.X>

The denominator for each percentage is the number of patients in the full analysis set within the column

Source: Listing 16.x.x Path\Filename

Page x/y

This layout also applies to: Table 14.3.6.2 Concomitant Medications (Full Analysis Set)

Version date: 23 August 2018

Page 63 of 93

ABX464-101

Listing 16.2.1 Discontinued Patients and Reason for Withdrawal

ddMMMyyyy

Treatment	Centre/ Patient number	First dose date	Last dose date	Date of withdrawal	Main reason for withdrawal

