		**************************************	**************************************	*************	XXXXXXXXXXXX XX.X XXXXXXX XX.X XXXXXXXX	**************************************	**************************************	XXXXXXXXXXXXX XXXXXXXXXXXXXX XXXXXXXXXXXXXX XXXXXXXXXXXXXXXXXXXXXXXXXXXXXXXXXXXX

Etc

Page x/y

Version date: 23 August 2018

Page 87 of 93

Path\Filename

This layout also applies to: Listing 16.4.11 Concomitant Medications (Programming note: can have stop date as 'ongoing')

Version date: 23 August 2018

ABX464-101

Listing 16.4.12 Procedures/ Non-Drug Therapies

ddMMMyyyy

Centre/ Patient	Procedure /Therapy	Start date	Ongoing / End date	Given for pre- existing condition?	Given for adverse event?		
number				(Related medical history number)	(Related adverse event number)		
xxx-xxxx	*****	ddMMMyyyy	Yes / No (ddMMMyyyy)	Yes (xxx) / No	Yes (xxx) / No		
	xxxxxxxxxxxx	ddMMMyyyy	Yes / No (ddMMMyyyy)	Yes (xxx) / No	Yes (xxx) / No		
	*****	ddMMMyyyy	Yes / No (ddMMMyyyy)	Yes (xxx) / No	Yes (xxx) / No		
	Patient number	Patient number xxx-xxxx xxxxxxxxxxxxxxxxxxxxxxxxxxxx	Patient number xxx-xxxx xxxxxxxxxxxx ddMMMyyyy xxxxxxxxxxxxxxx ddMMMyyyy	Patient number date xxx-xxx xxxxxxxxxxxxxx ddMMMyyyy Yes / No (ddMMMyyyy) xxxxxxxxxxxxxxxx ddMMMyyyy Yes / No (ddMMyyyy) xxxxxxxxxxxxxxxxx ddMMMyyyy Yes / No	Patient number date existing condition? (Related medical history number) XXX-XXXX XXXXXXXXXXXX ddMMMyyyy Yes / No Yes (XXX) / No (ddMMMyyyy) XXXXXXXXXXXXXXXX ddMMMyyyy Yes / No Yes (XXX) / No Yes (XXX) / No		

Path\Filename

Version date: 23 August 2018

Page 89 of 93

ABX464-101

[figure not shown]
Listing 16.4.13 Pregnancy Test

ddMMMyyyy

Treatment	Centre/ Patient number	Visit	Test done	Reason not done	Date of test	Result
xxxxx	xxx-xxxx	Screening	Yes/No/Not applicable	*******	ddMMMyyyy	Positive/Negative
		xx	Yes/No/Not applicable	xxxxxxxxxxx	ddMMMyyyy	Positive/Negative
		xx*	Yes/No/Not applicable	*******	ddMMMyyyy	Positive/Negative
		xx	Yes/No/Not applicable	*********	ddMMMyyyy	Positive/Negative
		Etc				
Etc						
*Outside the	visit window					Page x/y
Path\Filename	•					

Version date: 23 August 2018

Page 90 of 93

Statistical Analysis Plan

ABX464-101

Listing 16.4.14 Laboratory and Other Assessment Samples Collection

ddMMMyyyy

Parameter xxxxxx	Treatment	Centre/ Patient number	Visit	Sample taken ng Yes/No	Reason not done	Date of test ddMMMyyyy	Result	Interpretation			
	xxxxx		Screening					Normal/ Abnormal CS/ Abnormal			

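### The SAP's prior and concomitant medication definitions leave out drugs that span first dose with a known later stop date

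*SAP*

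**What the plan says.** SAP 11.6 gives four rules.

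- Prior: "Prior medications are defined as all medications that started and stopped before date of first dose".
- A restriction on prior: "Only medications where the stop date is prior to date of first dose will be considered prior".
- A fallback: "If the stop date is unknown or incomplete and the medications cannot definitely be considered as stopped prior to date of first dose", the drug is treated as concomitant. No condition is placed on its start date.
- Concomitant: "Concomitant medications are defined as all medications that started on or after date of first dose".

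Tables 14.3.6.1 (prior) and 14.3.6.2 (concomitant) then count patients by ATC level and preferred term in the FAS. The footnote to the prior table shell is shorter than the text definition: "Medication that stopped prior to date of first dose". A programming note in SAP 15 allows 'ongoing' as a stop-date entry in Listing 16.4.11, the concomitant listing.

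On the clinical side, Protocol 3.1.1 says that "study drug (ABX464 or its matching placebo) will be added on top of this background therapy for the next 56 days". Protocol 4.2.1 sets stability periods for drugs already in use, for example: "Subjects who are on oral 5-aminosalicylic acid must have been on a stable dose ≥4 weeks before the screening visit".

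**The concern.** The prior definition looks at both dates and the concomitant definition looks only at the start date, so the two do not cover every case. The uncovered case is common in a trial that adds study drug to continuing treatment: started earlier, still taken after first dose.

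At stake is the description of what patients were taking during treatment, by drug and by arm. With 20 and 10 patients planned, a few unclassified steroid or immunosuppressant users could visibly change the apparent balance. Other drugs that span Day 0 bear on the reading of treatment-emergent adverse events, the primary endpoint. Protocol 6.9.2 also singles out CYP1A2 substrates as possible interactions.

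**Working it through.** No figure in the plan can be reproduced here, because the point is one of logic. Count days from first dose as Day 0, with S the start day and E the stop day.

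**The rules as written**

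- Prior: S < 0 and E < 0.
- Concomitant: S ≥ 0, or E unknown or incomplete and not definitely before Day 0.
- Left over: S < 0 with E known and E ≥ 0. No rule covers this case.

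The text does not say whether 'ongoing' counts as an unknown stop date. The note on Listing 16.4.11 does not settle it, since a drug started after Day 0 can also be ongoing.

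**Classification of eight illustrative patterns**

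| Start | Stop | 'Ongoing' a known status | 'Ongoing' an unknown stop | After the fix |
|---|---|---|---|---|
| -60 | -20 | prior | prior | prior |
| -60 | 0 | neither | neither | concomitant |
| -60 | 40 | neither | neither | concomitant |
| -60 | 56 | neither | neither | concomitant |
| -60 | ongoing | neither | concomitant | concomitant |
| -60 | unknown | concomitant | concomitant | concomitant |
| 0 | 30 | concomitant | concomitant | concomitant |
| 10 | ongoing | concomitant | concomitant | concomitant |

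Four of eight patterns fall in neither table on the strict reading of 'ongoing', three of eight on the lenient reading, and none after the fix. These are counts of test patterns, not of patients or records.

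**Why background therapy is exposed**

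Screening is at Day -14 ± 3, so Day -11 at the latest. Oral 5-ASA, azathioprine, 6-mercaptopurine and methotrexate must be stable for 4 weeks before that, so they started no later than Day -11 - 28 = Day -39. Oral corticosteroids, probiotics and antidiarrheals must be stable for 2 weeks, so no later than Day -11 - 14 = Day -25. All of these have S < 0 by design.

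Whether such a record is lost then depends on its stop entry. Corticosteroids give the clearest route. Protocol 3.1.1 and 3.1.2 describe tapering from week 4 over 4 weeks (Day 28 to Day 56), at the investigator's discretion. A baseline steroid record closed in that interval has S ≤ -25 and a known E ≥ 28, which is the uncovered pattern. If each taper step is entered as a new record, the later steps start after Day 0 and count as concomitant. The documents do not say how steps are recorded.

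**What else reports these drugs**

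- Table 14.1.6 gives concomitant corticosteroids yes/no by arm.
- Table 14.1.8 gives UC medication categories by arm, and its note asks for all possible categories.
- Both are baseline tables in the FAS, with no ATC class or preferred term and no view of use during treatment.
- Table 14.1.8 also uses the word concomitant, which SAP 11.6 alone defines. Taken literally, that definition excludes the baseline drugs the table is meant to show.
- No other summary table covers non-UC drugs that span Day 0.
- The medication listings are 16.4.10 (prior) and 16.4.11 (concomitant). If they are built from the same definitions, the uncovered records have no assigned listing, although SAP 10.1 says eCRF data will be listed.

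**The case against.** A reader might infer that all stable background UC therapy vanishes from the medication summaries, that eligibility makes the omission 100%, and that balance between arms cannot be judged. The documents do not support this, for four reasons.

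- The fallback rule sends unknown or incomplete stop dates to concomitant whatever the start date. Stable background therapy is the kind most likely to have no stop date, and treating 'ongoing' the same way is a reasonable reading.
- The eligibility rules show that therapy began before Day 0. They do not show that its records carry a known stop date on or after Day 0, so they yield no percentage.
- Tables 14.1.6 and 14.1.8 show steroid use and UC drug categories by arm. Corticosteroid use is also a randomisation stratum, and the remission and adverse-event comparisons are both planned as stratified tests.
- The prior-table footnote and the restriction on prior suggest that everything not stopped before first dose was meant to be concomitant. A programmer may well code it that way.

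All four points limit the size of the problem, but none closes the gap. The likely intent is contradicted by the explicit definition of concomitant, and a known later stop date remains uncovered however 'ongoing' is handled.

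**Conclusion.** The point holds in this limited form. As written, the SAP 11.6 definitions are not exhaustive. A medication started before first dose with a known stop date on or after it belongs to neither Table 14.3.6.1 nor Table 14.3.6.2, and the same is true of an ongoing one on a strict reading. Background UC therapy is directly exposed and only partly covered elsewhere; non-UC drugs that span Day 0 have no other summary.

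The number of records affected cannot be derived from the documents. It depends on how 'ongoing' is coded, how taper steps are entered, and when patients stop their drugs. The conclusion assumes that the tables are programmed from the text of SAP 11.6 and not from the shell footnote. The effect is confined to descriptive reporting by ATC class and preferred term; no primary, efficacy or safety test uses these tables.

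**What to change.** Replace the concomitant definition in SAP 11.6 with: *all medications not definitely stopped before the date of first dose, that is, those started on or after that date, and those started before it that are ongoing or stopped on or after it*. Keep the prior definition and the rule for unknown or incomplete stop dates.

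A drug stopped before first dose must also have started before it, so the two classes then split on the stop date alone and every record falls in exactly one. Apply the same definitions to Listings 16.4.10 and 16.4.11, and state that Table 14.1.8 refers to UC medication in use at baseline.

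The cost is one SAP sentence and one line of code, plus the short note on Table 14.1.8. No data collection changes. Protocol section 9 requires SAP amendments to be documented and signed before final database lock.
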